e. Study time points: Participants will be followed prospectively in hospital with daily measures of calorie and supplement intake and weight from admission through discharge. Patients will be discharged when medically stable, with the primary criterion of heart rate ≥ 45 bpm for least 24 hr. Full medical stability defined as HR ≥ 45 bpm for 24 hrs, temperature ≥ 35.6°C for 24 hrs, ≥ 75% of mBMI, BP ≥ 90/45 mmHg for 24 hrs or if systolic BP < 90 then asymptomatic and all else stable, orthostatic change in HR ≤ 35 bpm or if > 35 then asymptomatic and all else stable; and orthostatic change in SBP ≤ 20 mmHg or if > 20 then asymptomatic and all else stable.

Timing of Procedures: Table 1

	INPATIENT			OUTPATIENT FOLLOW---UP				
	Admit	Daily	DC*	10 dy	1 Mo	3 Mo	6 Mo	12 Mo
MEDICINE/NURSING PROCEDURES								
Weight	SOC	SOC	SOC	X	X	X	X	X
Height	SOC			X	X	X	X	X
Vital Signs	SOC	SOC	SOC	X	X	X	X	X
Electrolyte monitoring ¥	SOC	X	SOC					
NUTRITION PROCEDURES								
24---hr food recall	X			X	X	X	X	X
QUESTIONNAIRE ADMINISTRATION								
EDE-Q	X		X		X	X	X	X
HCUMS survey				X	X	X	X	X
Demogr & Eating Disorder	X							

Follow-up form				X	X	X	X	X
----------------	--	--	--	---	---	---	---	---

* DC = discharge; SOC = Standard Of Care; Rnd = Randomization; ¥ SOC is every other day; we will monitor daily as part of Aim 2.

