3.2. Data Collection

Other than the treatment we are testing (HCR vs. LCR), patients will receive SOC in the hospital. Thus, as shown in **Table 1**, the vast majority of procedures in hospital are SOC. Follow-up visits, on the other hand, are for the purpose of collecting data and will be scheduled at the designated time points.

- a. **Baseline data collection:** The following covariates will be collected upon admission, prior to randomization.
 - (1) Demographics and eating disorder history: an intake form will be self-administered (with study coordinator as proctor, 15 min) to assess: highest body weight, lowest body, date of onset (to calculate length of illness and rapidity of weight loss), family history of eating disorder, self-reported race/ethnicity, maternal education and zipcode (to indicate socioeconomic status), date of birth.
 - (2) Eating Disorder Examination-Questionnaire (EDE-Q): is a standardized research interview that measures eating disorders psychopathology. [name] (co-I, UCSF) has used this tool extensively in RCTs examining psychotherapeutic modalities and long-term recovery in AN and BN and to categorize lower and higher risk study participants. He will oversee the psychological aspects of this study, including the EDE-Q.
 - (3) Food recall: dietary intake for the day prior to hospital admission will be assessed with a 24-hr food recall by the Research RD and analyzed via Nutrition Data System for Research (NDS-R) for total kcal and macronutrient profile. Dietary Density (DDS) and Variety Scores (DVS) will be calculated since acceptance of more energy dense and variety of foods in hospital has been shown to predict recovery at 8 mo.
 - (4) Severity of illness: %mBMI and HR on admission
 - (5) Health Care Utilization and Missed School (HCUMS) Survey: This proctored interview draws from established tools to assess cost, and has been tailored for AN and integrated with the follow-up form (above). In addition to "other care", it assesses health care utilization in the 6 months prior to admission including medications, physician visits, dental visits, ER visits and laboratory testing. It will be administered by trained research staff, who will document parent- and participant-reported care, supplemented with dates, doses, and other details available in the medical record.

b. Data collection daily in Hospital:

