- (1) SOC in hospital: Participants will be followed daily in hospital. Consistent with SOC for these patients, night time HR will be assessed with continuous cardiac monitoring throughout hospital stay, temperature will be measured orally and BP will be measured every 4-8 hr. Postural changes will be assessed with supine measurements (after 5 min), followed by standing measurements (after 2 min). When multiple vital signs measures are taken per protocol during one hospital day or one outpatient clinic visit, the most deviant value (lowest HR, lowest BP, greatest increase in HR and greatest decrease in BP on orthostatic changes, lowest Temp) will be recorded. Weight is measured every morning upon waking after voiding on an electronic scale, with the subject wearing only a hospital gown. Height will be measured within 24 hours of admission with wall-mounted stadiometer. Electrolytes will be monitored per SOC as described above in 3.1.c.
- (2) Study in hospital: Participants at both sites will complete the questionnaires above.
- c. **Data collection during follow-up:** Participants will return for five study follow-up visits through 12

months post-discharge and complete the following procedures:

- (1) Anthropometrics and vital signs: Height, weight and vital signs will be measured according to the in-hospital protocol by trained medical staff with standard equipment. Vital sign measures will be taken after a 20-min rest to minimize the influence of activity required to attend the visit (e.g. walk from car). After resting, vital signs will be measured in the research center with standard, calibrated equipment and with postural changes according to the procedure above. Data will be entered directly into the electronic data capture system with fillable and constrained sections for anthropometric measures and vital signs to minimize error.
- (2) Food recall: dietary intake for one full day during the week of each follow-up visit will be assessed with a 24-hr food recall by the Research Dietitian.

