- (3) HCUMS Survey: As described above, this proctored survey will assess utilization of health care such as re-hospitalizations since the time of the study-related hospitalization, participation in eating disorder treatment programs, medications, missed school, missed work, and other direct and indirect costs associated with eating disorder care since the time of each prior follow-up visit. The HCUMS will document medications pertinent to recovery measures (menses and psychopathology), including medications, current mental health care, other medical and psychological/psychiatric care ("other care") outside of our medical centers (e.g. residential care, psychiatric hospitalization). Psychotherapy modality and adherence may be important prognostic covariates of long-term outcomes in this open follow-up study.

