Aim 3. Cost Effectiveness (CE): A decision tree of treatment costs, AEs, health care utilized (including rehospitalizations), and remission will compare the CE between the two study arms. The main CE outcome is incremental cost per additional adolescent remitted. Health care utilization will be costed using national data sources such as acquisition costs for medications, Kids-HCUP for hospitalizations, CPT codes for physician visits and mental health visits, and internet-based costs for lab tests. We will use 2014 US costs and not charges. Indirect costs including missed school and workdays will be assessed and costed using national estimates of wages and salaries of this age group from the Bureau of Labor Statistics, in order to estimate loss of leisure time (school) or salary

time (work).

We will determine the incremental CE ratio (ICER) as:

$$\text{ICER} = \text{CostLCR-CostHCR}/\text{Number RecoveredLCR-Number RecoveredHCR}.$$

Effectiveness will also be indicated by cost of rehospitalizations avoided (ie, rehospitalizations in LCR-HCR). We will determine the net monetary benefit (NB) of each treatment option as: $\text{NB} = \text{Effectiveness} \times \text{Willingness To Pay (WTP)} - \text{Cost}$. A positive difference in NB between treatments indicates CE. We will also calculate an acceptability curve to demonstrate how parameter uncertainty affects the likelihood of selecting the optimal treatment at a given WTP threshold. Cost of treatment will be determined by initial hospitalization and 12 mo follow-up costs (not charges) including AEs and rehospitalizations. The HCUMS follow-up survey will assess indirect costs such as lost school and/or work (wages) using national data sources (see **C.2.c.(2)**).

Effectiveness will be determined per aim 1A; ICER will also use time (incremental cost per additional day of recovery time over 12 mo). Cost efficacy will be assessed with short-term outcomes at end of hospitalization. Per Aim 1B, cost-efficacy will be assessed with other short-term outcomes at the end of treatment (hospitalization period). Cost-efficacy will be defined as hospital cost or charges associated with length of stay; group differences will be compared with Wilcoxon rank sum test.

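### Table 1 omits the admission HCUMS that section 3.2.a requires, and Aim 3 makes no use of the pre-admission utilisation it would record

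*Combined protocol and SAP*

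**What the plan says.** Protocol section 3.2.a opens its baseline list with "The following covariates will be collected upon admission, prior to randomization". The HCUMS is item (5), and for the baseline administration "it assesses health care utilization in the 6 months prior to admission". Section 3.2.b(2), on study procedures in hospital, adds that "Participants at both sites will complete the questionnaires above".

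Table 1 in section 3.1.e gives a different schedule. Its HCUMS row reads "HCUMS survey X X X X X", with the cells for admission, daily and discharge empty. The food recall row, by contrast, reads "24---hr food recall X X X X X X", and its first mark is under Admit.

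Section 3.2.c(3) describes the follow-up HCUMS. It covers events such as "re-hospitalizations since the time of the study-related hospitalization", and other costs since each preceding visit.

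On the use of the data, SAP section 2.2, Aim 3 states: "Cost of treatment will be determined by initial hospitalization and 12 mo follow-up costs". It then sets out a decision tree, a ratio ICER, net monetary benefit, an acceptability curve and a Wilcoxon rank sum test for hospital cost. Pre-admission utilisation does not appear.

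**The concern.** The text and the schedule disagree on whether a baseline measurement is taken. Staff often work from the schedule table. If they do so here, utilisation before admission is either not asked about or asked about at the first outpatient visit. By then the family has been told the assignment (section 2.2 of the protocol) and has been through an unblinded treatment. Part of the survey is self- or parent-reported, so the timing of recall matters.

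The second issue is that the protocol calls these items covariates, yet Aim 3 gives this one no role. Earlier use of care is a natural candidate predictor of later cost. In a trial of 120, arms can differ on it by chance, and the cost comparison as written has no means of allowing for that.

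**Working it through.** **Step 1: is the missing Admit mark real?** Table 1 has eight columns: Admit, Daily, DC, 10 dy, 1 Mo, 3 Mo, 6 Mo, 12 Mo. Placing each row's marks against them gives:

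| Row | Marks | Columns |
|---|---|---|
| HCUMS | 5 | 10 dy, 1, 3, 6, 12 Mo |
| Follow-up form | 5 | 10 dy, 1, 3, 6, 12 Mo |
| 24-hr food recall | 6 | Admit, then the same five |
| EDE-Q | 6 | Admit, DC, 1, 3, 6, 12 Mo |

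Section 3.2.c says "Participants will return for five study follow-up visits through 12" months. Five marks for five visits leave none for admission, and neighbouring rows with a baseline assessment keep theirs. A text-extraction fault is therefore unlikely. Appendix Table 1 records no change to HCUMS timing.

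**Step 2: could the follow-up survey fill the gap?** Not by its stated window. Section 3.2.c(3) starts the clock at the study hospitalisation or the preceding visit, so the six months before admission fall outside it.

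**Step 3: is the covariate used anywhere for cost?** Adjustment appears in Aim 1A (unbalanced covariates in the remission models), in Aim 1B (a Cox model if an important covariate is unbalanced) and in SAP section 2.5 (secondary analyses for covariates linked to dropout). None of these names Aim 3.

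**Step 4: what would adjustment gain?** The plan gives no figure to reproduce. Let r be the correlation between baseline 6-month cost and 12-month cost; it is an assumption throughout. With linear adjustment, the variance of the arm difference in mean cost is multiplied by 1 − r², equivalent to 1/(1 − r²) times the participants.

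| r | 1 − r² | Variance removed | 1/(1 − r²) |
|---|---|---|---|
| 0.1 | 0.99 | 1% | 1.01 |
| 0.2 | 0.96 | 4% | 1.04 |
| 0.3 | 0.91 | 9% | 1.10 |
| 0.5 | 0.75 | 25% | 1.33 |

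**Step 5: how large could chance imbalance be?** With 60 per arm, the 95% range of a standardised baseline difference is ±1.96 × √(2/60) = ±0.36 SD. An imbalance at that limit moves the unadjusted cost difference by r × 0.36 SD: 0.04 SD at r = 0.1, 0.07 at 0.2, 0.11 at 0.3 and 0.18 at 0.5.

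**Step 6: which Aim 3 results benefit?** The SAP defines net benefit as effectiveness times willingness to pay (WTP), minus cost. Writing ΔE and ΔC for the arm differences in effectiveness and cost, the variance of the net-benefit difference is WTP² × Var(ΔE) + Var(ΔC) − 2 × WTP × Cov(ΔE, ΔC). Adjusting cost leaves the first term untouched, so net benefit gains only in part. The Wilcoxon test does not gain.

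**The case against.** The best defence is that the text is clear and the table is merely incomplete. Sections 3.2.a and 3.2.b(2) both direct collection in hospital. Section 3.2.a(5) also says the survey is combined with the follow-up form, and the two Table 1 rows match mark for mark, so the table may show only the follow-up version. Its footnote defines an abbreviation for randomisation that appears nowhere in the table as read, which could be leftover text or something lost in reading. Survey answers are supplemented from the medical record, and consent covers records and billing data. All of this lowers the chance of real loss. It does not remove the contradiction, and reported care outside the record would still depend on when the family was asked.

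On analysis, index-stay plus follow-up cost is the proper quantity for a randomised comparison, and leaving out earlier cost is legitimate. That stands.

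A reader might infer three stronger things that the documents do not support:

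- **That the cost comparison is biased.** Randomisation leaves it unbiased in expectation.
- **That adjustment is worth 10–33% more participants.** That needs r = 0.3–0.5, which no document supplies. Section 2.1.a excludes patients admitted in the previous six months, so prior inpatient cost is absent by design, while Aim 3 cost includes the index stay and rehospitalisations.
- **That one extra covariate would suffice.** Aim 3 contains no patient-level cost regression to add it to.

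**Conclusion.** The schedule contradiction holds and needs reconciling. Its practical effect is a possible loss of baseline utilisation, or its late collection once the arm is known, with partial recovery from records. The documents do not show that either happened.

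The absence of a baseline term in Aim 3 is a missed efficiency, not an error. Its size rests on the assumed r, on a roughly linear relation between prior and later cost, and on about 60 per arm. Because of the eligibility rule, the 1–4% variance reduction at r = 0.1–0.2 is more plausible than the 25% at r = 0.5. The point is minor: Aim 3 is not the primary aim, and the remission analysis is unaffected.

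**What to change.** 1. Mark the HCUMS at Admit in Table 1, so that the schedule agrees with section 3.2.a.
2. Add to SAP Aim 3 a patient-level regression of 12-month cost (index stay plus follow-up) on arm, baseline 6-month cost and site. Use the adjusted arm difference as the incremental cost in the ICER, net benefit and acceptability curve, and report the unadjusted result beside it.
3. Appendix Table 2 records the short-term database as locked on 07/31/2019, so correcting Table 1 may come too late to change collection. In that case, report when pre-admission use was actually recorded, and adjust only for values obtained before randomisation or taken from records that predate it.

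The cost is one table cell, one additional cost model, and the work of costing the six months before admission. The survey is already listed at baseline in the text, so the burden on participants is no more than section 3.2.a already asks.

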3.3. Safety

This study begins with a hospitalization as per SOC for patients who are medically unstable with malnutrition secondary to AN. Patients will be admitted to the adolescent medicine service if they are deemed medically unstable per published criteria. Once admitted, patients will be eligible for study enrollment. The treatment (HCR or LCR) is limited to the hospital stay. Aside from the questionnaires at both sites and daily (instead of every other day) electrolyte monitoring, all hospital procedures are consistent with SOC. After discharge, participants will be followed openly. They are required to be under a physician's care to ensure medical stability but not required to receive that care from us (however many do). Many patients have a psychiatrist to manage psychiatric co-morbidities such as anxiety and depression. If they receive care or hospitalization elsewhere they can still continue in the study and we will collect that with our follow-up form.

- a. Prospective monitoring of AEs: Aim 2 specifies three electrolyte abnormalities that will be monitored prospectively in all participants and documented as described in **3.1.c.&d.**: hypophosphatemia (<3 mg/dL), 2B) hypomagnesaemia (≤ 1.7 mg/dL), and 2C) hypokalemia (<3.5 mEq/L).
- b. Data and Safety Monitoring Board (DSMB): As a multi-center clinical trial comparing treatments, the proposed study is required to have a DSMB according to the NICHD policy for clinical research monitoring. The purpose of the DSMB is to ensure the safety of participants and validity of the trial. We will draft a DSM Plan using the NICHD template.

STATISTICAL ANALYSIS PLAN (most recent change May 26, 2019)

Multi-Center Randomized Controlled Trial of Refeeding in Anorexia Nervosa

1. Aims and Objectives

Our study has three main aims. We will compare:

AIM 1: Efficacy of LCR vs. HCR. We hypothesize that LCR and HCR will differ by *achievement and maintenance of* (1A) clinical remission during 12 mo follow-up, defined by achievement of both-(i) weight \geq 95% median BMI (MBMI) for age and sex, and (ii) Eating Disorder Examination-Questionnaire (EDE-Q) global score within 1 SD of clinical norm, and (1B) medical stability during initial hospitalization, defined by published vital sign thresholds.

AIM 2: Safety of LCR vs. HCR during initial hospitalization. We hypothesize that LCR and HCR will *not* differ by *incidence of* 2A) hypophosphatemia (<3 mg/dL), 2B) hypomagnesaemia (≤ 1.7 mg/dL), and 2C) hypokalemia (<3.5 mEq/L).

AIM 3: Cost-effectiveness (CE) of LCR vs. HCR. We hypothesize that HCR will be more cost-effective than LCR, as determined by cost (including costs of initial and re-hospitalizations, 12 mo follow-up, other care, and safety/adverse events (AEs) and effectiveness per adolescent recovered (defined in AIM 1A and B).

2. Statistical Methods

2.1. Pool of participants

a. Projected pool of eligible participants and accrual rate: At Stanford, in 2012 there were 295 admissions to the dedicated inpatient eating disorders unit, with approximately 36% of patients meeting DSM-4 criteria for AN; 100 similar patients were admitted at UCSF. With the broader eligibility criteria also including DSM-5, we anticipate at least 40% of patients (120 per yr at Stanford and 40 at UCSF) will be eligible. Of those who are eligible, we estimate that at least 50% will agree to participate and thus we will not attempt to achieve equal enrollment across sites. We will accrue 3-4 participants per mo over 3 yr until N=120 is reached and retain 85% of this sample through 12 mo as shown in open follow-up studies of participants with AN.

b. Commitments of Site PIs, Research Teams, and Participants: Both site PIs have successfully recruited and retained AN participants in research projects and seen them to completion and publication. Furthermore, co-I [name] is a faculty biostatistician with extensive experience in clinical trials. She will lead the DCC, aiming to ensure the trial is designed, executed, and analyzed without bias. Patient incentives to participate will emphasize the value of their contributions to medical research and remuneration for their time.

c. Data Analyses:

Sample Description: The study sample will be summarized and described (e.g., mean \pm SD) by stratification factor and baseline covariates to confirm general balance by arm and data will be summarized for completeness of follow-up (e.g., length of stay, last visit).

2.2. Outcomes

The primary analysis of the study adopts a modified intent-to-treat (mITT) approach to compare outcomes between randomized HCR and LCR participants who received treatment for at least one day. Patients who are ineligible post randomization, provide no assent after parent's consent, or withdraw before receiving any treatment, will not be included in the mITT analysis for reasons of data unavailability, ethics and clinical relevance. Sensitivity analyses will be conducted to check that 1) withdrawal patients are not different from patients in both groups included in mITT in baseline covariates; and 2) including withdrawal patients in the analyses will not change results and conclusion of mITT analyses. The sensitivity analyses will provide us

reassurance of mITT results.

Aim 1A: Primary (long-term) efficacy outcome. A (generalized) linear mixed-effects regression model (GLMM) will compare study arms with respect to achievement and maintenance of clinical remission. Clinical remission is defined as the combination of mBMI and EDE-Q score at mo 1,3,6,12 (separate analyses below) and measured at 1, 3, 6, and 12 months as 1) clinically remitted (yes or no) and 2) weight recovered (percent of mBMI). The models will include time, treatment group, time*treatment group interaction, and unbalanced baseline covariates if any as fixed effects, while sites and patients will be included as random effects to account for the correlation due to clustering. The time*treatment group interaction provides mITT effect of HCR compared to LCR on clinical remission over time. The average remission rates and scores and their 95% confidence intervals (CIs) will be estimated from the model. GLMM accounts for the fluctuating nature of mBMI and EDE-Q in AN and uses all available data with missing at random assumption, instead of a stronger assumption of missing completely at random required in other models. Aim 1 models will be supplemented with secondary analyses: (i) potential moderators at baseline (included in regression models as main effects and interactions with period and time), may include DSM-5 criteria and EDE-Q thresholds of risk and (ii) potential mediators at follow-up (included as time-dependent covariates), may include food recall (DDS and DVS), healthcare utilization, or incidence of AEs. In addition, separate mixed-effects models will analyze continuous versions of mBMI and EDE-Q to describe longitudinal trajectories.

Aim 1B: Secondary (short-term) efficacy outcome: Time to restore and maintain medical stability in hospital is defined as days to reverse the medical instability indicators for hospitalization in adolescents with eating disorders. A six-point index will adjudicate daily medical stability: 1.) 24-hour heart rate (HR) ≥ 45 bpm, 2.) systolic blood pressure (SBP) ≥ 90 mmHg, 3.) temperature $\geq 35.6^\circ$ C, 4.) orthostatic increase in HR ≤ 35 bpm, 5.) orthostatic decrease in systolic BP ≤ 20 mmHg, and 6.) $\geq 75\%$ of mBMI. Each of the six criteria were scored as "1" if met, "0" if unmet and missing (not scored) if not measured. Medical stability was considered restored when all criteria were stable for 24 hours, allowing a maximum of two missing values (i.e. participants were considered stable if meeting 4 of 4, 5 of 5 or 6 of 6 measured criteria). All randomized participants who receive at least one day of treatment, including those who withdraw at any time during the refeeding intervention, will be included in the mITT analysis. Specifically, survival analysis with log rank test will compare time to achieve medical stability by arm while accounting for the correlation within sites; participants who do not meet stability criteria by hospital discharge will be right-censored. In case of any important unbalanced covariate at baseline, Cox proportional hazard ratio model will be used to control for the potential bias due to the confounder. Additionally efficacy outcomes will include the proportion achieving medical stability in each arm, change in %mBMI as compared to baseline, and time to restore HR.

Aim 2. Safety: Primary indicator of safety will be incidence of the following electrolyte abnormalities during hospitalization: 2A) hypophosphatemia (<3 mg/dL), 2B) hypomagnesaemia (≤ 1.7 mg/dL), 2C) hypokalemia (< 3.5 mEq/L). These AEs will be tracked, recorded, reported to the DSMB for monitoring, and to the IRB and NIH as needed, according to the attached DSMP. Incidence of the electrolyte abnormalities and proportion receiving supplementation to correct electrolyte abnormalities will be compared by arm during hospitalization using Fisher's exact test. Additional safety outcomes: the proportion receiving electrolyte supplementation during the hospitalization between groups will be compared with Fisher's exact test; time to electrolyte nadir will be compared with Wilcoxon rank sum test.

Aim 3. Cost Effectiveness (CE): A decision tree of treatment costs, AEs, health care utilized (including rehospitalizations), and remission will compare the CE between the two study arms. The main CE outcome is incremental cost per additional adolescent remitted. Health care utilization will be costed using national data sources such as acquisition costs for medications, Kids-HCUP for hospitalizations, CPT codes for physician visits and mental health visits, and internet-based costs for lab tests. We will use 2014 US costs and not charges. Indirect costs including missed school and workdays will be assessed and costed using national estimates of wages and salaries of this age group from the Bureau of Labor Statistics, in order to estimate loss of leisure time (school) or salary

time (work).

We will determine the incremental CE ratio (ICER) as:

$$\text{ICER} = \text{CostLCR-CostHCR}/\text{Number RecoveredLCR-Number RecoveredHCR}.$$

Effectiveness will also be indicated by cost of rehospitalizations avoided (ie, rehospitalizations in LCR-HCR). We will determine the net monetary benefit (NB) of each treatment option as: $\text{NB} = \text{Effectiveness} \times \text{Willingness To Pay (WTP)} - \text{Cost}$. A positive difference in NB between treatments indicates CE. We will also calculate an acceptability curve to demonstrate how parameter uncertainty affects the likelihood of selecting the optimal treatment at a given WTP threshold. Cost of treatment will be determined by initial hospitalization and 12 mo follow-up costs (not charges) including AEs and rehospitalizations. The HCUMS follow-up survey will assess indirect costs such as lost school and/or work (wages) using national data sources (see **C.2.c.(2)**).

Effectiveness will be determined per aim 1A; ICER will also use time (incremental cost per additional day of recovery time over 12 mo). Cost efficacy will be assessed with short-term outcomes at end of hospitalization. Per Aim 1B, cost-efficacy will be assessed with other short-term outcomes at the end of treatment (hospitalization period). Cost-efficacy will be defined as hospital cost or charges associated with length of stay; group differences will be compared with Wilcoxon rank sum test.

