2.1. Study Population

- a. **Inclusion/Exclusion:** Adolescents hospitalized for medical instability secondary to malnutrition will be eligible as follows. **Inclusion criteria:** diagnosis of AN, atypical AN, age 12-24 years, no hospital admissions for the previous six months, and meet hospitalization criteria (daytime HR < 50 bpm or night time HR < 45 bpm, BP <90/45 mmHg, temperature < 35.6° C or orthostasis defined by increase in HR > 35 bpm or decrease in systolic BP > 20 mmHg from lying to standing). **Exclusion criteria:** diagnosis of bulimia nervosa [DSM-5], currently in remission (as defined by weight and EDE-Q score per Aim 1), admission for food refusal without malnutrition, current pregnancy, chronic disease (e.g. immune/endocrine disorders, pulmonary, cardiac, or renal disease), current suicidality or psychosis.
- b. **Participant recruitment and consent:** Participants and their parents will sign assent (for those < 18 yr) and consent, respectively within 24 hr of hospitalization. This may occur in the clinic when they are deemed medically unstable and waiting transfer to the hospital or in the hospital if admitted directly. Consent will include permission to review all medical records, to review hospital billing data, and to contact for future research projects. If a participant turns 18 yr while enrolled, s/he will be reconsented. Participants 18 years of age and older are able to consent themselves; thus we will request verbal consent from their parents to complete parent surveys.

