2.2. Randomization

Participants will be stratified by site and randomly assigned 1:1 to the two intervention strategies within 24 hr of hospital admission. The Data Coordination Center (DCC) will provide a secure unpredictable allocation sequence (e.g. A B B A ...) which will be programmed into a secure electronic study tracking system for assignment of each accrued participant. The sequences will be generated using block size of two to four to maximize balance between arms throughout accrual while ensuring the sequences remain unpredictable. As patients consent to study participation, clinical-research staff will assign the next available study ID number in sequence, identify the allocated intervention arm, and inform participants and their families of the assignment. In turn, the clinical research staff will provide the linked study ID number and Medical Record Number to the DCC, which will store this Personal Health Information in a HIPAA-compliant manner along with the intervention assignment.

3. Study Procedures

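### The arm can be released and disclosed before a minor's documented assent and a completed eligibility check, and the SAP then excludes such patients after randomization

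*Combined protocol and SAP*

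**What the plan says.** **Trigger for allocation.** Protocol 2.2 (Randomization) states: "As patients consent to study participation, clinical-research staff will assign the next available study ID number in sequence, identify the allocated intervention arm". In the same step staff "identify the allocated intervention arm, and inform participants and their families of the assignment". Neither a signed assent nor a completed eligibility check is named as a condition.

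**Timing.** Protocol 2.1 b states: "Participants and their parents will sign assent (for those < 18 yr) and consent, respectively within 24 hr of hospitalization". Protocol 2.2 has participants "randomly assigned 1:1 to the two intervention strategies within 24 hr of hospital admission". The two windows coincide, and neither section sets the order of the steps.

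**Analysis set.** SAP 2.2 (Outcomes) sets out to "compare outcomes between randomized HCR and LCR participants who received treatment for at least one day". It then removes three groups. Two are "Patients who are ineligible post randomization, provide no assent after parent's consent". The third follows in the same sentence: "or withdraw before receiving any treatment, will not be included in the mITT analysis for reasons of data unavailability, ethics and clinical relevance".

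**Related text.** Protocol 2 says treatment is not blinded. Protocol 3.2 a collects baseline covariates, including the EDE-Q and %mBMI, before randomization. SAP 2.2 plans two sensitivity checks for patients who withdraw: a baseline comparison with those analysed, and a rerun that includes them.

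**The concern.** Randomization protects the comparison only from the moment of allocation onward. If the arm is released while assent or eligibility is still open, the decision that settles it is taken with the arm known. There are two routes, and they differ:

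- **Refusal by the minor.** A participant under 18 who is asked to assent after hearing the calorie assignment may decline because of it.
- **Exclusion by staff.** A patient ruled ineligible after allocation does not choose to leave. The risk is that the ruling is made by people who know the arm.

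Either could occur at different rates in the two arms, whereas SAP 2.3 assumes dropout that does not differ by arm. Analysis cannot fully repair this. A minor who never assented may have no usable outcome, and the SAP itself cites data unavailability and ethics for these exclusions. This makes the timing of release a separate matter from the definition of the analysis set.

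**Working it through.** **Step 1. Order of events, sections side by side.**

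| Step | Where | Condition stated |
|---|---|---|
| Consent and assent | Protocol 2.1 b | Within 24 hr of hospitalization |
| Baseline covariates (EDE-Q, %mBMI) | Protocol 3.2 a | Before randomization |
| Allocation and disclosure | Protocol 2.2 | As patients consent; within 24 hr of admission |
| Exclusion of ineligible or non-assenting patients | SAP 2.2 | From a set defined among randomized participants |

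If assent always preceded allocation, a non-assenting minor would never be randomized, and a set defined among randomized participants would not need to exclude that minor. The exclusion therefore suggests that the other order was foreseen. For ineligibility, the SAP says outright that it can be found after randomization.

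**Step 2. The plan's own figure.** The plan gives no figure for these losses. The nearest is in SAP 2.3: 60 per arm, 8% vs 28%, two-sided 0.05, 80% power (cross-sectional case). With the pooled normal approximation:

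- pooled rate = (0.08 + 0.28)/2 = 0.18
- null SE = √(2 × 0.18 × 0.82/60) = 0.0701
- alternative SE = √((0.08 × 0.92 + 0.28 × 0.72)/60) = 0.0677
- power = Φ((0.20 − 1.96 × 0.0701)/0.0677) = 82.2%

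This agrees with the stated 80% given the table's 2-point steps: 8% vs 26% gives 75.3%, so 8% vs 28% is the first step to reach 80%. That figure is not in dispute.

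**Step 3. Power if participants are lost (loss rates assumed).** Same formula, equal losses in both arms, before any allowance for the planned 15% loss to follow-up:

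| Assumed loss per arm | n per arm | Power, 8% vs 28% |
|---|---|---|
| 0% | 60 | 82.2% |
| 5% | 57 | 80.2% |
| 10% | 54 | 78.0% |
| 15% | 51 | 75.6% |

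**Step 4. Shift in one arm's rate (illustration).** Each loss is 1/60 = 1.7% of an arm. Take 28% of 60, about 17 remitters, and remove only non-remitters from that arm:

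- none lost: 17/60 = 28.3%
- 1 lost: 17/59 = 28.8%
- 6 lost: 17/54 = 31.5%

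**Step 5. The same mechanism with no true difference (assumed).** Set true remission at 18% in both arms, the mean of 8% and 28%, and let a share *l* of one arm leave, none of whom would have remitted. The observed rate is 0.18/(1 − *l*):

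- *l* = 5%: 18.9%, a spurious difference of 0.9 points
- *l* = 10%: 20.0%, 2.0 points
- *l* = 15%: 21.2%, 3.2 points

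If the leavers would have remitted at 9% instead of 0%, the 10% case gives (0.18 − 0.10 × 0.09)/0.90 = 19.0%, a 1.0-point difference.

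**The case against.** The case on the other side is substantial.

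- **The order is not stated.** In SAP 2.2 the reference to randomization is attached to ineligibility. The missing assent is placed only after the parent's consent, so the sentence might be listing consented families who were never allocated. In Protocol 2.2 it is the patient who consents, which can be read as requiring the minor's own agreement first. This stands: allocation before assent is an inference. On that reading, though, the exclusion has no work to do in a set defined among randomized participants, and the two sections still need to be reconciled.
- **Part of the safeguard exists.** The EDE-Q and %mBMI are due before randomization, so the inputs for the remission exclusion should be in hand. This also stands, but nothing requires the check against Protocol 2.1 to be completed before the arm is released.
- **Sensitivity analyses are planned.** They are, but they are worded for patients who withdraw. Whether they reach ineligible or non-assenting patients is unclear, and data may not exist.
- **The effect is small.** Even the one-sided illustration moves a rate by about 3 points, against a 20-point target difference. This stands, and no count supports anything larger.
- **It may be late.** Appendix Table 2 records the randomization code broken and the short-term database locked in 2019. The documents do not state enrolment status, but a new condition on allocation may have little left to act on. The reporting part would still apply.

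A reader might infer that the plan instructs staff to allocate minors before they assent. The documents do not say so.

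**Conclusion.** The point holds in a limited form. As written, the plan allows the arm to be released and disclosed before assent and eligibility are documented, and it provides for excluding the resulting cases after randomization. For ineligibility this is explicit; for assent it is inferred. These exclusions can depend on the arm in an open-label trial, and the planned sensitivity analyses cover them only in part.

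The likely size is modest and unknown. The illustrations give a shift of up to about 3 points in one arm's rate, and a power loss of about 2 to 7 points for losses of 5–15% per arm. They rest on assumed loss rates. The rate shifts also assume losses confined to one arm and, for the largest values, that no leaver would have remitted.

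Two stronger conclusions are not supported. One is that bias has occurred: the documents report no such losses. The other is that earlier assent and eligibility checks would remove every loss between allocation and treatment. Eligible, assented participants can still withdraw on hearing their arm, some ineligibility comes to light only later, and SAP 2.2 separately excludes those who withdraw before treatment.

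**What to change.** **Protocol 2.2.** Have the electronic tracking system release an assignment only when three items are recorded: signed consent, assent for participants under 18, and a completed checklist of the Protocol 2.1 criteria. The remission item can use the EDE-Q and %mBMI already collected before randomization. Allocation stays within the existing 24-hour window. State plainly that the minor's assent precedes allocation, so that Protocol 2.1, Protocol 2.2 and SAP 2.2 agree.

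**SAP 2.2.** Treat any remaining no-assent or ineligible case as a protocol deviation and report it by arm and reason. If enrolment has finished, this is the part that can still be carried out.

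**Cost.** One required field set in an existing system, one protocol sentence and one SAP sentence. The downside is that allocation may come a few hours later within the same window.
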